6.8.6.7 Device Performance

Device-related terminology

- Initial device implant: The first IDDD implant that a patient ever receives.
- Partial device revision: Surgical revision/replacement of one or more component(s) of the device; other component(s) of the original device remain implanted and are not affected (e.g., port revision).
- Full device revision: The device is removed (explanted) in its entirety and a completely new device is implanted, including complete device removal with immediate replacement and delayed device implant after previous removal.
- Complete device removal with immediate replacement: Immediately implant of a new device after a device had been completely removed.
- Delayed device implant after previous removal: Implant of a new device after a previous device had been completely removed without immediate replacement on a separate and earlier occasion.
- Complete device removal without replacement: All parts of the device (both port and catheter) are removed and there is no new device implant.
- Device adjustment: surgical procedure of the device that is not a port replacement or full device revision.
- Device malfunction: The device does not perform as intended, based on the description in the device's Instructions for Use, but does not require either a partial or full device revision. If at the time of a scheduled dosing it is not possible to administer a full medication dosage as per the standard administration steps detailed in the device's Instructions for Use due to a device related issue, the IDDD will be declared a device malfunction. A device malfunction could be resolved without the need for a full or partial surgical revision. Programmatically it is when the malfunction date is present and outcome of malfunction is resolved.
- Device failure: When the device irreversibly fails to perform as intended and cannot be corrected without a device surgical intervention of either a partial or full device revision or removal. The IDDD will be declared a device failure, starting from the date of the initial malfunction that persists leading to the above surgical intervention. IDDDs that are considered to be malfunctioning at the end of the study will be categorized as Failures. For programming purposes, a device failure is when the malfunction date is present and outcome of malfunction is either ongoing or device failure (Surgical Procedure). The date of the device failure is the date of the initial malfunction.

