- IDDD longevity: Total number of IDDD failures and explant divided by the total time at risk across all subjects in weeks (sum of time to IDDD failure or the last injection if not failed at the end of the data cut or explant date, from initial implantation, delayed implantation, or revision for all IDDDs).

Device Performance Analyses

SOPH-A-PORT[®] safety and performance will be summarized for IDDD-implanted patients in Safety Population. The number and proportion of patients of the following categories and the corresponding event count and event percentage will be summarized:

- Patients who had the initial implant only (i.e., no additional surgeries)
- Patients who had any post-initial implantation device surgeries
- Patients who had any type of difficulty associated with the implant procedure (e.g., difficulty accessing spinal canal, etc)

IDDD-related surgical procedure details for initial implants, complete removal with immediate replacement, and delayed implantation across all IDDD implantations for all patients will be summarized by failed or not failed IDDDs and overall, including incision region (paramedian vs. other), identification of the catheter passer used (Phoenix Neuro vs. other), number of suture wings implanted, suture wing configuration, interspace for catheter insertion into lumbar spine (L1-2, L2-3, L3-4, L4-5, L5-S1), spinal vertebral level of catheter tip (cervical, thoracic, lumbar and sacral), use of a purse string suture, use of the guidewire, orientation of the Tuohy needle and clinical site.

The number and proportion of patients who had at least one abnormal IDDD radiological assessment finding and the number of abnormal findings from the IDDD radiological assessments will be also summarized by types of the abnormality.

The number and proportion of patients and IDDDs with total malfunctions (including failure and malfunctions) as well as the corresponding event numbers will be presented. The types of IDDD malfunctions and the reasons for IDDD failures reported by the site and the Adjudication Committee will be summarized at the patient, IDDD and event level.

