The annual event rate of IDDD failures and malfunctions will be calculated for each patient and the descriptive statistics will be summarized. The overall IDDD failure rate and its 95% CI will be presented. The overall IDDD failure rate is calculated as the total number of IDDD failures for all patients divided by the total IDDD time at risk, which is defined as the total time to IDDD failure or the last injection if IDDD is not failed at the end of the study, from initial implantation, or full device revision for all IDDDs. The overall IDDD malfunction rate is defined in the same manner.

The IDDD longevity (time to failure in weeks) and time to first total malfunction, for all implanted IDDDs, will be analyzed using the KM method. A new port identifies a new IDDD, starting from the date of implantation (either an initial implantation, a partial or full revision, or a

delayed device implant after previous removal). The time to IDDD failure (weeks) or total malfunction will be obtained by subtracting the date of the IDDD kit implantation from the date of IDDD failure (i.e., the initial malfunction date that persists leading to surgical intervention) or first total malfunction plus 1, and divided by 7, one decimal will be kept. IDDDs which did not fail or malfunction will be censored at the last study drug injection date for each IDDD. The number of IDDDs at risk, the cumulative number of IDDDs failed, censored, and the cumulative probability of failure with its standard error will be summarized in a table at each event time.

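### The pooled IDDD failure rate restarts device time only at a full revision, which conflicts with two other rules in the same SAP section and, read literally, overstates the rate after a partial revision

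*SAP*

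**What the plan says.** SAP 6.8.6.7 (Device Performance) states when device time starts in three places.

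- **Pooled failure rate.** "The overall IDDD failure rate is calculated as the total number of IDDD failures for all patients divided by the total IDDD time at risk". That time ends at failure, or at the last injection "if IDDD is not failed at the end of the study, from initial implantation, or full device revision for all IDDDs". The pooled malfunction rate is said to follow the same pattern.
- **Device-level Kaplan-Meier (KM) analysis, next paragraph.** "A new port identifies a new IDDD, starting from the date of implantation (either an initial implantation, a partial or full revision", with delayed implant also listed.
- **Terminology list.** "IDDD longevity: Total number of IDDD failures and explant divided by the total time at risk across all subjects in weeks", with time counted "from initial implantation, delayed implantation, or revision for all IDDDs".

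Four definitions in the terminology list matter here. Full revision means replacement of the whole device, "including complete device removal with immediate replacement and delayed device implant after previous removal". A failure is a fault that "cannot be corrected without a device surgical intervention of either a partial or full device revision or removal", and it is dated at the initial malfunction. A partial revision replaces one or more components and leaves the others in place; port revision is given only as an example. Longevity is defined in this list as events over time, whereas the KM paragraphs of the same section and Protocol 10.7.7.3 use the word for the weeks until failure.

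**The concern.** Full revision already takes in immediate and delayed replacement, so partial revision is the only restart missing from the pooled rate. On the literal wording, the clock stops at a failure and does not start again after a partial repair. A later failure in that patient still counts. The numerator is complete and the denominator is cut short.

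Device safety and performance is a stated objective (Protocol 2.4), and this device was adopted because its predecessor failed often (Protocol 1.3). The pooled rate and its 95% CI speak directly to that question. As written, two programmers could each follow part of the section and report different rates from the same data.

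**Working it through.** The documents state no failure rate, failure count or time at risk, so there is no figure to reproduce. The check compares the rules and then illustrates the consequence.

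**Rules side by side (SAP 6.8.6.7)**

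| Quantity | Time starts at | Partial revision included? |
|---|---|---|
| Pooled failure rate | initial implant, full revision | no |
| Device-level KM | initial implant, partial or full revision, delayed implant | yes, if a new port is placed |
| Terminology-list ratio | initial implant, delayed implant, any revision | yes |

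The end points differ too: only the terminology list names the explant date.

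**One patient.** Assumed course in weeks from implant: failure at 20, partial revision at 22, last injection at 46. Rate = failures / weeks at risk × 52.

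- No further failure. Literal: 1/20 × 52 = 2.60 per year. With restart: 20 + (46 − 22) = 44 weeks, and 1/44 × 52 = 1.18.
- Second failure at week 40. Literal: 2/20 × 52 = 5.20. With restart: 20 + (40 − 22) = 38 weeks, and 2/38 × 52 = 2.74.

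**Trial scale.** Inputs: 32 IT-treated patients (SAP 4.1), with implant at Week 2 and last scheduled injection at Week 48 (Protocol Section 7), so 48 − 2 = 46 weeks each and 32 × 46 = 1472 device-weeks. Assume k patients fail at mid-course (week 23), are partially revised at once and do not fail again. The literal denominator is 1472 − 23k.

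| k | Literal weeks | Literal rate per year | Rate with restart | Overstatement |
|---|---|---|---|---|
| 4 | 1380 | 0.151 | 0.141 | 7% |
| 8 | 1288 | 0.323 | 0.283 | 14% |
| 16 | 1104 | 0.754 | 0.565 | 33% |

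**Range.** Under a constant hazard, let m be the expected failures per patient over 46 weeks and q the share of failures handled by partial revision. Then literal rate / rate with restart = 1 / [(1 − q) + q(1 − e^−m)/m]. For m = 0.25 and q = 0.25 this is 1.03; for m = 0.5 and q = 0.5 it is 1.12; for m = 1 and q = 1 it is 1.58. At q = 0 it is exactly 1. Simulation agreed with the formula. The values of m, q, k and the failure times are assumptions, not document figures.

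**Other readings of the same sentence.**

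- If a repaired device is treated as not failed at study end, its time is kept. In the one-failure example the rate is 1/46 × 52 = 1.13.
- If the repaired device is timed again from its initial implant, weeks are counted twice and the rate is too low. In the two-failure example the weeks are 20 + 40 = 60, and 2/60 × 52 = 1.73 against 2.74. In simulation at m = 0.5 and q = 0.5, it gave 0.509 against 0.568 per year.

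**The case against.** The strongest reply is that the text does not settle the direction. The pooled time is summed over all IDDDs, and the next paragraph says that a new port makes a new IDDD, so a programmer could carry that rule back and keep the time. This stands in part: upward bias follows from the literal wording, not from every reading. It does not rescue the sentence, which lists its start points and leaves one out.

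Two limits on size also stand. Time is lost only for partial revisions that follow a failure, because a partial revision without one does not stop the clock. And the frequency of such repairs appears nowhere in the documents, so the percentages are illustrations and not evidence of an actual bias.

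The consequence is contained. Safety analyses are descriptive and untested (Protocol 10.7, SAP 6.8), and the pooled rate is not among the device measures in Protocol 10.7.7.3. The KM analyses, the proportions and counts, the by-patient listing and the event timeline do not use this denominator. A reader might infer that the rate ought to match the KM result. It need not, since they are different summaries; the valid requirement is that both use the same start dates.

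A reader might also infer from the terminology list that a higher reported longevity would mean a worse device. No planned output is described that way: each analysis using the word glosses it in place as time until failure. The mismatch is one of labelling.

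**Conclusion.** The point holds as an inconsistency in the exposure rule. On its literal wording, the pooled failure rate and its 95% CI are computed on too little device time whenever a failure is repaired by partial revision, and the pooled malfunction rate inherits the same start points. The literal rate can never be lower than the one with restart, and the two are equal if no such repair occurs. The illustrative overstatement is 3% to 58% for m from 0.25 to 1 and q from 0.25 to 1, both assumed.

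It would be tempting to conclude that the reported failure rate will be overstated by some definite amount. The documents do not support that: they give no count of partial revisions, and the wording admits readings that keep the time or count it twice. The effect is confined to descriptive device-performance rates, and efficacy inference is untouched.

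**What to change.** State one time-at-risk rule for the pooled failure and malfunction rates, consistent with the device-level KM analysis:

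- **Start** at initial implantation, delayed implantation, and any partial or full revision that restores function after a failure, including a catheter-only revision that places no new port. Restarting only when a new port is placed would leave the same error for catheter-only repairs.
- **End** at failure, explant or last injection.
- Say that a partial revision with no preceding failure neither drops nor repeats device time.
- In the KM text, where a new port defines a new IDDD, state how catheter-only revisions are handled.

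As an editorial correction, rename the events-over-time ratio in the terminology list a failure/explant rate and keep longevity for time to failure.

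The cost is SAP wording and the matching program specification. The KM analysis and the device timeline already need the implant, revision, failure and injection dates, so no new data are required.

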	
Behavior Index and its subscales (Internalizing, Externalizing)
 
Exploratory efficacy endpoint
 
 • Slope estimate from the linear regression of GCA scores over time for each subject 
Additional efficacy endpoint for substudy only
 
 • Observed value in raw score, age equivalents versus chronological age, as well as DQ, composite score and percentile for the three scales of the BSID-III (Motor [Fine, Gross], Language [Receptive, Expressive], Cognitive) for substudy only 
Pharmacokinetic and Pharmacodynamic endpoints
 
 • Serum concentration of idursulfase and serum PK parameters after IT administration • CSF concentration of idursulfase prior to each monthly IT administration • Change from baseline in the concentration of GAG in CSF 
Safety Assessments
 
Safety will be assessed during the study by collection of adverse events (by type, severity, and relationship to treatment [idursulfase-IT, the IDDD, device surgical procedure, or IT administration process] and IV Elaprase infusion), changes in clinical laboratory testing (serum chemistry, hematology, urinalysis), physical and neurological examination, vital signs, 12-lead ECG, CSF laboratory parameters (chemistries, cell counts), anti-idursulfase antibodies in CSF and serum, and determination of antibodies having enzyme neutralizing activity.
 
SOPH-A-PORT[®] Mini S Device Assessments
 
The SOPH-A-PORT Mini S device will be evaluated using assessments of device implantation, device function, device longevity and adverse events associated with the implant surgery or device. Those data will be collected on the patient's electronic case report form (eCRF) from the time of initial implantation and continue throughout the study as long as the SOPH-A-PORT[®] Mini S remains implanted.
 
Health Status Assessment
 
Health status dimensions as obtained by the EQ-5D questionnaire: mobility, self-care, usual activities, pain/discomfort, and anxiety/depression.

Number of Subjects	
Pivotal study
 
 • 48 male patients (32 IT treated and 16 No IT treatment) are planned.

	
Substudy
 
 • There is no pre-specified number of patients planned. The enrollment will conclude when enrollment of patients in the pivotal study closes.

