The time from initial implant surgery to first IDDD failure and the time to first malfunction will be analyzed using the Kaplan Meier (KM) method for each patient who is in the Safety Population with IDDD implanted. The time to first IDDD failure or malfunction will be obtained by subtracting the date of the first IDDD implantation for the patient from the date of first failure or malfunction plus 1, divided by 7, and one decimal will be kept. Patients without an IDDD failure or malfunction will be censored at their last study drug injection date. The 25th percentile (Q1), median and 75th percentile (Q3) of the time to first failure or malfunction distribution and the 95% confidence interval (CI) will be presented together with the KM plots. A by-patient listing of the device failure and malfunction data will be displayed.

The IDDD longevity (time to failure in weeks) and time to first total malfunction, for all implanted IDDDs, will be plotted using the KM method. The 25th percentile (Q1), median and 75th percentile (Q3) of the time to failure or total malfunction distribution and the 95% CI will also be presented together with the KM plots.

The time (weeks) from IDDD implantation to failure/continuing function will be plotted as a horizontal bar chart for each device sorted by duration of each device implantation (time from the implantation of the corresponding IDDD), longest on top.

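### The all-device Kaplan-Meier curve and the overall failure and malfunction rates pool first and replacement ports from the same boy without allowing for clustering, so their intervals can be too narrow and the curve can be too pessimistic for a first port

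*SAP*

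**What the plan says.** The unit of the device-level analysis in SAP 6.8.6.7 is the port: "A new port identifies a new IDDD, starting from the date of implantation". Replacement ports therefore join the same data set as first ports, each with its own time zero. Longevity and time to first total malfunction, "for all implanted IDDDs, will be analyzed using the KM method", and "the cumulative probability of failure with its standard error will be summarized in a table at each event time". Later in the section the pooled curves are plotted with "The 25th percentile (Q1), median and 75th percentile (Q3) of the time to failure or total malfunction distribution and the 95% CI".

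The section also gives a pooled rate: "The overall IDDD failure rate and its 95% CI will be presented". It is defined as the "total number of IDDD failures for all patients divided by the total IDDD time at risk", and the malfunction rate is built in the same way.

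No patient cluster, robust variance, frailty term or bootstrap is named for any of these outputs. The CI method for the rate is not stated, and SAP Appendix II has no sample code for the device analyses.

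The same section plans outputs with one record per boy: a Kaplan-Meier analysis from initial implant to first failure and to first malfunction, and annual event rates calculated for each patient. Protocol 10.7.7.3 likewise plans both the patient-level and the all-device curves.

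**The concern.** Ports in the same boy share anatomy, activity and usually the surgical site. The documents treat such factors as relevant. Protocol 6.7.3 warns that certain movements can damage or displace components, and SAP 6.8.6.7 tabulates surgical details and clinical site by whether the device failed. If risk differs between boys for these reasons, two things follow.

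First, ports within a boy are positively correlated, and an SE that counts them as independent is too small. Second, a boy contributes another port mainly after losing the previous one, so boys at higher risk are over-represented. The pooled curve then describes the mix of ports implanted, not the outlook for a newly implanted boy.

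The safety and performance of the device is a stated objective (Protocol 2.4, SAP 4.1). A printed SE or 95% CI is a statement of precision even in a descriptive analysis.

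**Working it through.** The documents give no failure rate, event count or CI width for this port, so there is no figure to reproduce. The size has to come from assumptions, shown here as a range.

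**Inputs from the documents**
- Boys who can supply ports: about 32 (SAP 4.1: "48 male patients (32 IT treated and 16 No IT treatment) are planned").
- Follow-up: implant at about Week 2, censoring at the last injection at about Week 48, so 48 − 2 = 46 weeks.

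**Assumed inputs**
- Failure rate λ of 0.25, 0.5 or 1.0 per device-year, with exponential device life.
- A gamma frailty per boy with mean 1 and variance θ of 0, 0.5, 1 or 2.
- Immediate replacement after failure.
- All 32 boys implanted on schedule.

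**Expected counts.** Device-years = 32 × 46 / 52.18 = 28.2. At λ = 0.5 this gives 14.1 failures and 32 + 14.1 = 46.1 ports. At 0.25 it gives 7.1 failures and 39.1 ports. At 1.0 it gives 28.2 failures and 60.2 ports.

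**Formulas**
- Greenwood: SE = S(t) · √Σ[d / (n(n − d))].
- Poisson interval for the rate: log rate ± 1.96 / √D, where D is total failures.
- Patient-clustered SE of the log rate: √[N/(N − 1) · Σ(Dᵢ − rYᵢ)²] / D, summed over boys, where Dᵢ and Yᵢ are a boy's failures and device time and r is the overall rate.
- True first-port survival: (1 + θλt)^(−1/θ), or exp(−λt) when θ = 0. At 40 weeks, λ = 0.5 and θ = 1: λt = 0.5 × 40 / 52.18 = 0.383, so survival is 1 / 1.383 = 0.723.

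**Results.** There were 4000 simulated trials per row, and trials without a failure were left out. The true SE is the standard deviation across trials. Survival is at 40 weeks.

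| λ | θ | KM true/Greenwood SE | Rate true/Poisson SE | Poisson CI coverage | Clustered CI coverage | Pooled survival | First-port survival |
|---|---|---|---|---|---|---|---|
| 0.25 | 0 | 1.02 | 1.05 | 97.1% | 96.3% | 0.828 | 0.826 |
| 0.25 | 0.5 | 1.08 | 1.14 | 95.0% | 95.5% | 0.826 | 0.833 |
| 0.25 | 1 | 1.10 | 1.16 | 95.8% | 96.6% | 0.826 | 0.839 |
| 0.25 | 2 | 1.20 | 1.25 | 94.2% | 96.7% | 0.827 | 0.850 |
| 0.5 | 0 | 1.01 | 1.04 | 95.5% | 94.4% | 0.685 | 0.682 |
| 0.5 | 0.5 | 1.12 | 1.17 | 92.3% | 93.8% | 0.686 | 0.704 |
| 0.5 | 1 | 1.16 | 1.23 | 91.1% | 94.2% | 0.688 | 0.723 |
| 0.5 | 2 | 1.29 | 1.41 | 86.6% | 93.4% | 0.691 | 0.752 |
| 1.0 | 0 | 1.02 | 1.02 | 94.9% | 93.8% | 0.469 | 0.465 |
| 1.0 | 0.5 | 1.12 | 1.21 | 90.5% | 94.2% | 0.480 | 0.523 |
| 1.0 | 1 | 1.21 | 1.39 | 85.4% | 93.6% | 0.489 | 0.566 |
| 1.0 | 2 | 1.39 | 1.68 | 77.8% | 92.9% | 0.503 | 0.628 |

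**In interval terms** (λ = 0.5, θ = 1)
- The log-rate SE is 0.278 naive and 0.342 true. The 95% limits are the rate divided and multiplied by exp(1.96 × 0.278) = 1.72, against exp(1.96 × 0.342) = 1.95. For a rate of 0.5 that is 0.29 to 0.86 against 0.26 to 0.98.
- The KM half-width is 1.96 × 0.0716 = 0.140 against 1.96 × 0.0832 = 0.163.

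**Variant.** An 8-week gap before re-implantation (λ = 0.5, θ = 1) reduces the ratios to 1.09 (KM) and 1.16 (rate). Poisson coverage is 93%, and pooled survival is 0.699 against 0.723.

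**First ports only.** A KM with one port per boy has a true/Greenwood SE ratio of 1.00 to 1.04 in every setting.

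Only failure was simulated. The argument carries over to malfunction, but its size there was not computed.

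**The case against.** The strongest reply is that the sound analysis is already in the plan. Time to first failure, with one record per boy, is specified in SAP 6.8.6.7 with quartiles, 95% CIs and plots. The per-patient rates do not pool ports across boys either, and SAP 6.8 makes all safety analyses descriptive. This stands. It leaves the device-level intervals and the question of which curve leads, and it means no efficacy conclusion or success criterion is touched.

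Four stronger readings are tempting, and the documents do not support them.

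- **Replacement occurs only after failure.** SAP 6.8.6.7 defines a full revision by removal and re-implantation, whatever the reason, and its longevity definition counts explants beside failures. Protocol 1.3 records removals of the earlier device for wound problems.
- **The intervals are too narrow as a matter of fact.** That needs between-boy variation and enough replacements, and the documents quantify neither. Some expected device effects in Protocol Appendix 5, such as a badly positioned catheter or a failed component, belong to one implant rather than to the boy. At θ = 0 the naive SEs are nearly right.
- **The SAP chose a wrong interval for the rate.** It names no method, so independence there is an inference.
- **Very low coverage of the pooled curve shows how narrow its interval is.** At λ = 1.0 and θ = 1, the Greenwood interval covers the first-port value in only 72.9% of trials but covers the pooled curve's own mean in 88.4%. Most of the shortfall is a different target, which a wider SE would not repair.

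**Conclusion.** The point holds conditionally. The SAP pools several ports per boy and names no method for the dependence. With between-boy variation, the default SEs and CIs understate uncertainty. At the middle assumption of 0.5 failures per device-year, the shortfall is moderate: the ratios of 1.12 to 1.29 and 1.17 to 1.41 above. At 0.25 per year the rate CI still covers 94% to 96%. At 1.0 per year and frailty variance 2, coverage drops to 78%.

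The pooled curve separately overstates failure for a first port, by 3.5 percentage points of 40-week survival at 0.5 per year and variance 1 (0.723 − 0.688).

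These sizes rest on exponential device life, gamma frailty, re-entry through failure, and 32 boys followed for 46 weeks. Delayed implantation, which Protocol 8.3.1 describes for some patients in the USA, would reduce device time and replacements. This is an improvement to the device reporting and does not threaten the trial's conclusions.

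**What to change.** In SAP 6.8.6.7:

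1. State the CI method for every device-level output. Compute the SEs and CIs of the all-device KM, including the quartiles, and of the overall failure and malfunction rates with patient-clustered variance or a bootstrap that resamples boys. In the simulations the clustered rate CI covered 93% to 97% with immediate replacement.
2. Label the already planned time-to-first-failure KM as the main device-survival curve, and say how a first port removed without failure is handled there. As worded, a boy's time appears to run on through his next port.
3. In the all-device KM, show first and replacement ports separately. Clustered intervals alone do not remove the over-representation of boys who lose ports.

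The cost is a few sentences in the SAP, a little programming and slightly wider intervals. No new data are needed.

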1.3 Overview of Results of Phase I/II Studies

The safety and tolerability of ascending doses (1, 10, or 30 mg) of intrathecally administered idursulfase-IT were investigated in the first-in-human study HGT-HIT-045, a randomized, open-label, no-treatment controlled Phase I/II study in which idursulfase-IT was administered once monthly to pediatric MPS II patients via a surgically implanted IDDD (PORT-A-CATH[®] II Low Profile[™] Intrathecal Implantable Access System [PORT-A-CATH]) for 6 months in conjunction with once weekly IV infusion of Elaprase. Eligible patients who completed HGT-HIT-045 are receiving monthly IT injections of idursulfase-IT, in conjunction with Elaprase therapy, in extension study HGT-HIT-046. Across the HGT-HIT-045 and HGT-HIT-046 studies, long-term safety, pharmacokinetics (PK), and pharmacodynamics (PD) (effect on GAG concentration in CSF) have been evaluated. Effects of IT administration of idursulfase-IT on neurodevelopmental health have been evaluated using standardized tests of cognitive and adaptive functions.

Based on the data available from HGT-HIT-045 and HGT-HIT-046, idursulfase-IT has been found to be well tolerated at all doses administered without safety concerns related to the study drug. There have been no deaths or discontinuations due to adverse events (AEs) in either study, and no serious adverse events related to idursulfase-IT. The majority of serious adverse events in both studies have been associated with the PORT-A-CATH device, and designated as serious because of the requirement for overnight hospitalization for surgical revision/removal of the IDDD. The events related to the use of the IDDD included surgical removal and replacement of the device because of mechanical failures, primarily connector pin breaks and catheter slippage, to overnight admissions to the clinical site for a suspected device infection, and device removal because of wound issues.

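### The SAP counts explants in its definition of IDDD longevity but not in the longevity Kaplan-Meier, so a device removed for a complication with no malfunction record is an event under one rule and censored under the other

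*SAP*

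**What the plan says.** All the SAP text is in 6.8.6.7 Device Performance.

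- **Definition of longevity** (device-related terminology): "IDDD longevity: Total number of IDDD failures and explant divided by the total time at risk across all subjects in weeks". Time at risk runs to failure, or else to "the last injection if not failed at the end of the data cut or explant date". No reason for explant is specified.
- **Programming rule for failure** (same list): "a device failure is when the malfunction date is present and outcome of malfunction is either ongoing or device failure (Surgical Procedure"). The failure is dated at the initial malfunction.
- **Longevity as analysed** (device performance analyses): "The IDDD longevity (time to failure in weeks) and time to first total malfunction, for all implanted IDDDs, will be analyzed using the KM method". The event date is "the initial malfunction date that persists leading to surgical intervention".
- **Censoring in that analysis**: "IDDDs which did not fail or malfunction will be censored at the last study drug injection date for each IDDD". Explants have no rule of their own. The longevity plot later in the section uses the same time-to-failure label.
- **Overall failure rate**: "total number of IDDD failures for all patients divided by the total IDDD time at risk".
- **Per-patient curve**: time from first implant to first failure, with patients who have none censored at their own last injection.

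Protocol 10.7.7.3 also labels longevity as time to failure and has no explant event. Protocol 3.5 names device longevity as one of the device assessments.

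**The concern.** A device can be lost without a recorded malfunction. Protocol 7.14.1.3 lists skin erosion, implant rejection and tract infection as IDDD-related adverse events, as items separate from device failure. Protocol Appendix 5 adds wound dehiscence to the expected effects. Protocol 1.3 reports "device removal because of wound issues" in Phase I/II, although with a different device (PORT-A-CATH). An infected or eroding port may still deliver doses, so nothing in the definitions forces a malfunction date onto it.

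If such a device is explanted, the curve labelled longevity treats it as having the same prospects as a device still implanted and working. A reader of that curve would take it to show how long devices last, while losses that the SAP's own definition counts are left out. Device safety and performance is a stated objective (Protocol 2.4), so the label matters even though nothing is tested.

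**Working it through.** **Tracing one device.** Take a device explanted for a complication, with no malfunction date recorded.

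| Step in SAP 6.8.6.7 | Result for this device |
|---|---|
| Failure, as programmed | No: needs a malfunction date |
| Malfunction, as programmed | No: needs a malfunction date |
| Longevity by definition | Counted in the numerator; explant date can end time at risk |
| Longevity by per-device Kaplan-Meier | Censored at its last injection, before the explant |
| Overall failure rate | Not counted, as the name implies |
| Per-patient curve, if re-implanted and dosed again | Patient stays at risk through later injections |
| Explanted before any injection | Censoring date undefined in the per-device curve |

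**Size.** The documents give no expected failures, explants or longevity figure, so there is none to reproduce. What follows is an illustration.

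Inputs: 32 devices, one per planned treated patient (SAP 4.1). Implantation is at Week 2 and dosing at Weeks 4 to 48 every 4 weeks (Protocol 8.3), so injections fall at weeks 2, 6, ..., 46 after implant. Assumed, not in the documents: 4 failures at weeks 9.2, 18.4, 27.6 and 36.8; 2 complication explants at weeks 15.8 and 31.2; the other 26 devices censored at week 46.

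*Planned rule.* The explants are censored at their last injections, weeks 14 and 30. The numbers at risk at the four failures are 32, 30, 29 and 27.

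1 − (31/32)(29/30)(28/29)(26/27) = 1 − 0.871 = **12.9%**

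*Explants counted as events.* Nothing is censored before week 46, so the estimate is (4 + 2)/32 = **18.8%**.

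*Explant as a competing event.* Cumulative incidence is 4/32 = 12.5% for failure and 2/32 = 6.25% for complication explant, together 18.75%.

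*As rates.* Time at risk is 92 + 44 + 26 × 46 = 1,332 weeks under the planned rule, and 92 + 47 + 1,196 = 1,335 weeks when explants end their own time. The failure rate is 4/1,332 × 52 = 0.156 per device-year. The rate with explants in the numerator is 6/1,335 × 52 = 0.234.

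The same calculation with other assumed counts, events spread evenly, gives these week-46 probabilities (planned rule vs explants counted):

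| Failures | 0 explants | 1 explant | 2 explants | 4 explants |
|---|---|---|---|---|
| 2 | 6.2% vs 6.2% | 6.4% vs 9.4% | 6.6% vs 12.5% | 6.7% vs 18.8% |
| 4 | 12.5% vs 12.5% | 12.7% vs 15.6% | 12.9% vs 18.8% | 13.6% vs 25.0% |
| 8 | 25.0% vs 25.0% | 25.5% vs 28.1% | 26.0% vs 31.2% | 27.1% vs 37.5% |

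Across the cells with at least one such explant, the gap is about 3 to 12 percentage points.

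**The case against.** The best defence is that the curve is labelled time to failure, failure is defined, and the protocol uses the same label. A curve that counts failures is not wrong for leaving out other losses. The gap above comes from changing the event, and it does not demonstrate dependent censoring. This stands for a curve called time to failure. It does not answer a section that calls the same curve longevity after defining longevity with explants included.

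Some stronger readings are tempting, and the documents do not support them:

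- *Every complication explant is missed.* Under SAP 6.8.6.7 and Protocol 7.5.4, a device-related issue that prevents a full scheduled dose is a malfunction, and an irreversible one that needs surgery is a failure. The prose definition of failure also mentions removal. The gap is confined to devices explanted with no malfunction ever recorded. The malfunction/failure form is not in the documents, so their number cannot be judged.
- *The overall failure rate is in error.* It counts failures, as its name says.
- *The per-patient curve censors a patient at explant.* A patient re-implanted and dosed again remains at risk.
- *A device explanted before its first injection contributes no time.* The per-device rule leaves the date undefined.
- *Phase I/II shows how often this will happen.* It involved another device, whose mechanical replacements were mainly due to connector breaks and catheter slippage.

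Removals are also visible elsewhere: device surgeries, end-of-study device status, the timeline plot and the adverse event tables. That limits the harm but does not correct the longevity curve. Nor is the terminology-list definition a ready replacement, because it counts explants of any kind, including the removals on leaving the study that Protocol 7.5.4 foresees.

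**Conclusion.** The contradiction holds: one named quantity has two event rules, and a complication explant with no malfunction record falls between them. The longevity curve would then omit device losses that the SAP's definition counts. With 4 failures and 2 such explants among 32 devices, it would show 12.9% lost by week 46 against 18.8%; with none, the rules agree. The counts and timings are assumptions, so these figures show what is possible and do not predict an amount of bias. A reader might infer that the plan is set to halve the reported device loss. The documents do not support that, because the frequency is unknown and dose-blocking complications that lead to surgery are already failures. SAP 6.8 makes all safety analyses descriptive, and neither efficacy inference nor type I error is affected. The change is still worth making, because it is specific and cheap.

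**What to change.** Reconcile the definition, the Kaplan-Meier text and the plot text in SAP 6.8.6.7:

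1. Define the longevity event as device failure, or explant for a device- or procedure-related complication, dated at the failure or the explant. Use it in the definition, the per-device analysis and the plot.
2. Censor planned removals, for example on leaving the study, which the definition as written would count as events.
3. Keep the time-to-failure curve and the overall failure rate, labelled as failure only, and show complication explant as a competing event alongside that curve.
4. State how a device explanted before its first injection contributes time at risk.
5. State how a patient explanted for a complication and re-implanted is handled in the per-patient curve.

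The cost is SAP wording and some programming. One point needs confirming: Protocol 7.5.4 puts details of removal on the CRF but does not say that the reason is captured, and item 1 depends on it.
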